1.2 Sustained Pain Relief

The ad-hoc sustained pain relief endpoints were:

- Sustained Pain Relief 3 to 24 hours
- Sustained Pain Relief 4 to 24 hours
- Sustained Pain Relief 3 to 48 hours
- Sustained Pain Relief 4 to 48 hours

Sustained pain relief for the above time periods were defined in a manner similar to that used previously for sustained pain relief from 2 to 24 hours and 2 to 48 hours.

Sustained pain relief was assessed using the number of mITT subjects who experienced no or mild headache pain (response of 0 or 1 on the Likert scale) at all time points from the starting time point (3 or 4 hours post-dose) through the ending time point (24 or 48 hours post-dose). Subjects with missing pain scores at 1 or fewer time points, given that they had responses of no or mild pain at all other time points including the starting and ending time points (and 24 hours for periods through 48 hours), were considered as successes. Subjects with missing data at greater than 1 post-dose time point, missing data at either the starting or ending time point (or

24 hours for periods through 48 hours), or with any pain score greater than 1 were considered as failures.

1.3 Sustained Freedom from Most Bothersome Symptom

The ad-hoc sustained freedom from the MBS endpoints were:

- Sustained Freedom from MBS 2 to 24 hours
- Sustained Freedom from MBS 3 to 24 hours
- Sustained Freedom from MBS 4 to 24 hours
- Sustained Freedom from MBS 2 to 48 hours
- Sustained Freedom from MBS 3 to 48 hours
- Sustained Freedom from MBS 4 to 48 hours

Sustained freedom from MBS for these time periods is defined in a manner similar to that used for sustained pain freedom from 2 to 24 hours and 2 to 48 hours.

Sustained MBS freedom was assessed using the number of mITT subjects who did not have their MBS (response of absent) at all time points from the starting time point (2, 3 or 4 hours post-dose) through the ending time point (24 or 48 hours post-dose). Subjects with missing MBS scores at 1 or fewer time points, given that they had responses of absent MBS at all other time points including the starting and ending time points (and 24 hours for periods through 48 hours), were considered as successes. Subjects with missing data at greater than 1 post-dose time point, missing data at either the starting or ending time point (or 24 hours for periods through 48 hours), or with any MBS present at any time point in the period were considered as failures.

1.4 Sustained Freedom from Functional Disability

The ad-hoc sustained freedom from functional disability endpoints were:

- Sustained Freedom from Functional Disability 2 to 24 hours
- Sustained Freedom from Functional Disability 3 to 24 hours
- Sustained Freedom from Functional Disability 4 to 24 hours
- Sustained Freedom from Functional Disability 2 to 48 hours
- Sustained Freedom from Functional Disability 3 to 48 hours
- Sustained Freedom from Functional Disability 4 to 48 hours

Sustained freedom from functional disability for these time periods is defined in a manner similar to that used for sustained pain freedom from 2 to 24 hours and 2 to 48 hours.

Sustained freedom from functional disability was assessed using the number of mITT subjects who experienced normal functioning at all time points from the starting time point (2, 3 or 4 hours post-dose) through the ending time point (24 or 48 hours post-dose). Subjects with missing disability scores at 1 or fewer time points, given that they have responses of no disability at all other time points including the starting and ending time points (and 24 hours for periods through 48 hours), were considered as successes. Subjects with missing data at greater than 1 post-dose time point, missing data at either the starting or ending time point (or 24 hours for periods through 48 hours), or with any reported disability in the time period were classified as failures.

1.5 Sustained Freedom from Nausea

The ad-hoc sustained freedom from nausea endpoints were:

- Sustained Freedom from Nausea 2 to 24 hours
- Sustained Freedom from Nausea 3 to 24 hours
- Sustained Freedom from Nausea 4 to 24 hours
- Sustained Freedom from Nausea 2 to 48 hours
- Sustained Freedom from Nausea 3 to 48 hours
- Sustained Freedom from Nausea 4 to 48 hours

Sustained freedom from nausea for these time periods was defined in a manner similar to that used for sustained pain freedom from 2 to 24 hours and 2 to 48 hours. However, the analysis population was restricted to those subjects with nausea reported as present at the start of their treated migraine.

Sustained nausea freedom was assessed using the number of mITT subjects who had nausea present at baseline and did not report nausea (response of absent) at any time point from the starting time point (2, 3 or 4 hours post-dose) through the ending time point (24 or 48 hours post-dose). Subjects with missing nausea scores at 1 or fewer time points, given that they had responses of no nausea at all other time points including the starting and ending time points (and 24 hours for periods through 48 hours), were considered as successes. Subjects with missing data at greater than 1 post-dose time point, missing data at either the starting or ending time point (or 24 hours for periods through 48 hours), or with any nausea present at any time point in the period were considered as failures.

1.6 Sustained Freedom from Photophobia

The ad-hoc sustained freedom from photophobia endpoints are:

- Sustained Freedom from Photophobia 2 to 24 hours
- Sustained Freedom from Photophobia 3 to 24 hours
- Sustained Freedom from Photophobia 4 to 24 hours
- Sustained Freedom from Photophobia 2 to 48 hours
- Sustained Freedom from Photophobia 3 to 48 hours
- Sustained Freedom from Photophobia 4 to 48 hours

Sustained freedom from photophobia for these time periods was defined in a manner similar to that used for sustained freedom from nausea. The analysis population was restricted to those mITT subjects with photophobia reported as present at the start of their treated migraine.

Sustained photophobia freedom was assessed using the number of mITT subjects who had photophobia present at baseline and that did not report photophobia (response of absent) at any time point from the starting time point (2, 3 or 4 hours post-dose) through the ending time point (24 or 48 hours post-dose). Subjects with missing photophobia scores at 1 or fewer time points, given that they had responses of no photophobia at all other time points including the starting and ending time points (and 24 hours for periods through 48 hours), were considered as successes. Subjects with missing data at greater than 1 post-dose time point, missing data at either the starting or ending time point (or 24 hours for periods through 48 hours), or with any photophobia present at any time point in the period were considered as failures.

1.7 Sustained Freedom from Phonophobia

The ad-hoc sustained freedom from phonophobia endpoints are:

- Sustained Freedom from Phonophobia 2 to 24 hours
- Sustained Freedom from Phonophobia 3 to 24 hours
- Sustained Freedom from Phonophobia 4 to 24 hours
- Sustained Freedom from Phonophobia 2 to 48 hours
- Sustained Freedom from Phonophobia 3 to 48 hours
- Sustained Freedom from Phonophobia 4 to 48 hours

Sustained freedom from phonophobia for these time periods was defined in a manner similar to that used for sustained freedom from nausea. The analysis population was restricted to those mITT subjects with phonophobia reported as present at the start of their treated migraine.

Sustained phonophobia freedom was assessed using the number of mITT subjects who had phonophobia present at baseline and that did not report phonophobia (response of absent) at any time point from the starting time point (2, 3 or 4 hours post-dose) through the ending time point (24 or 48 hours post-dose). Subjects with missing phonophobia scores at 1 or fewer time points, given that they had responses of no phonophobia at all other time points including the starting and ending time points (and 24 hours for periods through 48 hours), were considered as successes. Subjects with missing data at greater than 1 post-dose time point, missing data at either the starting or ending time point (or 24 hours for periods through 48 hours), or with any phonophobia present at any time point in the period were considered as failures.

2 TIME TO EVENT ANALYSES

2.1 Time to Rescue Medication

Kaplan-Meier plots were created for the time to first use of rescue medication. The K-M plot covered the 24 hour period after dosing. Subjects who did not take rescue medication within 24 hours of dosing were censored at 24 hours and 1 minute. Regardless of pain or MBS response, subjects were considered at risk until the first use of rescue medication, loss to follow-up (last contact date), or the end of the 24 hour period, whichever came first. The analysis population consisted of mITT subjects.

Two tables were created to support the plot. The first table presented the median time to rescue medication along with 95% CIs calculated using the method of Brookmeyer and Crowley and the log-rank p-value. The second table presented the number of subjects at risk, with an event, censored, and the survival probability estimate (with 95% CI) for each period by treatment group.

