2.2 Randomization Methodology

The study will randomize approximately 1,200 subjects. The subjects will be randomized in a 1:1 ratio to receive rimegepant in a 75 mg tablet or matching placebo (see Figure 1). The randomization will be stratified by the use of prophylactic migraine medications (yes or no).

Figure 1: Study Schematic

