5.2.4 Adjustments for Covariates and Stratification

The randomization of subjects was stratified by the use of prophylactic migraine medication (yes or no). Hence, most analyses are stratified by the use or prophylactic medication.

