5.2.5 Multiple Comparisons

Type I error is controlled in this study by using a hierarchical gate-keeping procedure. First, the family of two co-primary endpoints is tested. If the co-primary endpoints are found to be significant, then secondary endpoints are tested in a fixed sequence. In particular, each co-primary endpoint will be tested for superiority to placebo at a two-sided alpha level of 0.05 without further adjustment for multiplicity. If the primary endpoint tests are both significant, then the following secondary endpoints will be tested in a fixed sequence, in the order shown, with each test conducted at p=0.05:

- 1. Photophobia Freedom at 2 hours
- 2. Phonophobia Freedom at 2 hours
- 3. Pain Relief at 2 hours
- 4. Nausea Freedom at 2 hours
- 5. Probability of Rescue Medication Use
- 6. Sustained Pain Freedom from 2 to 24 hours
- 7. Sustained Pain Relief from 2 to 24 hours
- 8. Sustained Pain Freedom from 2 to 48 hours
- 9. Sustained Pain Relief from 2 to 48 hours
- 10. Pain Relapse from 2 to 48 hours

11. Functional Disability at 2 hours

If a test in the hierarchy is not significant, then any further tests on endpoints in the sequence will have p-values presented only for descriptive purposes, and no conclusions will be drawn from those results.

For exploratory endpoints, no attempt will be made to adjust for multiplicity. Any exploratory endpoints for which p-values are produced will be evaluated at an unadjusted two-sided alpha level of 0.05 and presented only for descriptive purposes.

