2.2 Time to First Report of Absence of Various Symptoms

For each of the following variables, two sets of Kaplan-Meier plots and tables were created:

- Time to First Report of Absence of Most Bothersome Symptom
- Time to First Report of Absence of Nausea
- Time to First Report of Absence of Photophobia
- Time to First Report of Absence of Phonophobia
- Time to First Report of Return to Normal Functioning

The first set of plots and tables was similar to those created for the time to rescue medication (using actual time). For the second set of plots, nominal (planned time point) as opposed to actual time was used for clinical event times. Censoring was measured using actual time as in all previous plots.

For both sets of analyses, the analysis population for MBS and functional disability was the set of mITT subjects. The analysis population for nausea, phonophobia, and photophobia was the subset of mITT subjects that reported the symptom as present at the onset of their study migraine. The y-axis for all plots represents the probability of the occurrence of the event of interest, and therefore are increasing from left to right.

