3 PAIN AND MBS AT 3 HOURS POST DOSE

3.1 Pain Freedom at 3 Hours Post Dose

The between group difference in the percentage of subjects with pain freedom at 3 hours postdose was assessed by computing the "risk difference" between treatment groups. This was evaluated by computing the common risk difference, using CMH weights (sample size weights), stratified by the use of prophylactic migraine medication (yes or no). The risk difference was tested at a two-sided alpha level of 0.05. Missing data at 2 hours post-dose were imputed as failures (NC=F).

Results presented for this analysis included the following:

- Common risk difference with sample size, p-value, ASE, and 95% asymptotic CIs.
- Risk difference within each strata with sample size, p-value, ASE, and 95% asymptotic CIs.
- A plot of the risk differences within each strata, and common risk difference (similar to the risk difference plot produced by SAS Proc Freq).
- Common risk for each treatment with sample size, ASE, and 95% asymptotic CIs.

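### The log-rank test in SAP Appendix 3 names no stratification by prophylactic medication, the randomization factor; stratifying it costs almost nothing and gains a little power if that factor is prognostic

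*SAP*

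**What the plan says.** - **Randomization.** SAP 2.2 makes use of prophylactic migraine medication (yes or no) the stratification factor, with 1:1 allocation.
- **General rule.** SAP 5.2.4 draws the consequence from that: "Hence, most analyses are stratified by the use or prophylactic medication". It lists no exceptions.
- **Time to rescue.** Appendix 3, section 2.1 describes Kaplan-Meier curves over 24 hours in mITT subjects. One supporting table gives median times with confidence limits "calculated using the method of Brookmeyer and Crowley and the log-rank p-value". No strata are mentioned.
- **Symptom and functioning curves.** Appendix 3, section 2.2 names no test. It says "The first set of plots and tables was similar to those created for the time to rescue medication", using actual time. A second set uses nominal time for the events.
- **Contrast within the same appendix.** Section 3.1 (pain freedom at 3 hours) is explicit: the common risk difference is computed "using CMH weights (sample size weights), stratified by the use of prophylactic migraine medication (yes or no"). Sections 3.2 and 4.1 say the same.
- **Status.** SAP section 7 calls the Appendix 3 analyses supportive, and Appendix 4 labels their tables ad hoc. None is in the fixed sequence of SAP 5.2.5.

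**The concern.** When randomization is stratified on a factor that predicts the event, the arms are balanced on it by design. A plain log-rank test takes no account of that balance, so its variance estimate is too large. It also compares subjects of unequal prognosis within each risk set. Both effects make the test conservative.

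The mismatch is clearest for rescue medication. Rescue within 24 hours is fifth in the confirmatory sequence and is analysed (SAP 5.7.4.3) through the stratified outputs of SAP 5.7.3.1. Appendix 3, section 2.1 tests the same event in the same population over the same 24 hours, with no stated stratification. A reader who compares the two p-values cannot tell how much of any difference comes from timing information and how much from a different adjustment.

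What is at stake is a small amount of efficiency in descriptive p-values, and a clear account of what was tested.

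**Working it through.** **1. The plan's own figures.** The SAP states no power or event count for any log-rank test. Its only power statement (SAP 5.1) is more than 95% per co-primary endpoint with about 550 treated subjects per arm. For pain freedom, with the Phase 2b rates of 31.4% and 15.3% (Protocol 1.3.2.8):

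- Difference 0.161; pooled rate 0.2335.
- Null standard error √(2 × 0.2335 × 0.7665 / 550) = 0.02551.
- Alternative standard error √((0.314 × 0.686 + 0.153 × 0.847) / 550) = 0.02505.
- Power = Φ((0.161 − 1.96 × 0.02551) / 0.02505) = Φ(4.43), above 99.9%.

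The statement is reproduced. Ninety percent of 600 is 540 rather than 550, and power stays above 99.9% at 540. So 550 per arm is used below.

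**2. Which tables could carry the test.** Appendix 4 lists a Kaplan-Meier table and a median-time table for rescue (14.2.3.12.1 and .2). Section 2.1 puts the log-rank p-value in the median table. MBS, nausea, photophobia, phonophobia and normal functioning each have the same pair, once in actual and once in nominal time (14.2.3.13.1 to 14.2.3.17.4). That is 1 + 5 = 6 median tables if only the actual-time set follows the rescue format, and 1 + 5 × 2 = 11 if both do.

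**3. The two tests.** At each event time j, let d be events, n subjects at risk, and d₁ and n₁ the same in the rimegepant arm.

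- U = Σ(d₁ − d·n₁/n)
- V = Σ d·(n₁/n)(1 − n₁/n)(n − d)/(n − 1)
- Plain: reject if U²/V > 3.84, over all subjects.
- Stratified: compute U and V within users and non-users, and reject if (U_yes + U_no)²/(V_yes + V_no) > 3.84.

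**4. Simulation for time to rescue.** There were 550 subjects per arm, exact balance within strata, exponential times, censoring at 24 hours, and 4,000 trials per setting. The documents give none of the following, so all are assumed:

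- share on prophylaxis: 15%, 30% or 50%;
- 24-hour event proportion in placebo non-users: 30% or 60%, that is, hourly rates −ln(0.7)/24 = 0.0149 and −ln(0.4)/24 = 0.0382;
- treatment hazard ratio: 0.72 and 0.80 respectively, which gives about 80% power when prophylaxis has no effect;
- hazard ratio of prophylaxis on the event: 1, 1.5, 2 or 3.

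Ranges are over the six combinations of share and event proportion:

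| Prognostic HR | Type I error, plain | Type I error, stratified | Power, plain | Power, stratified | Gain (points) |
|---|---|---|---|---|---|
| 1 | 4.5–5.3% | 4.5–5.3% | 78.2–80.5% | 78.1–80.5% | −0.1 to 0.0 |
| 1.5 | 4.6–5.6% | 4.8–5.8% | 80.3–85.4% | 80.9–85.8% | 0.3 to 0.7 |
| 2 | 4.0–4.8% | 4.5–5.6% | 79.0–89.7% | 81.0–90.9% | 0.9 to 3.2 |
| 3 | 2.8–4.4% | 4.9–5.8% | 77.2–92.1% | 82.6–94.2% | 2.2 to 9.8 |

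The simulation standard error is about 0.35 points for type I error and 0.6 for each power. At 1.5 the gain is no larger than roughly one such error, although both tests ran on the same data and the sign was the same in all six settings. The highest plain type I error, 5.6%, is (5.625 − 5)/0.35 = 1.8 standard errors above nominal, so there is no sign of inflation.

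**5. A second set of assumptions.** With 1,100 subjects, 40% placebo rescue by 24 hours, treatment hazard ratio 0.78, 20% on prophylaxis and 3,000 trials, power is 72.5% plain and 73.3% stratified at a prognostic hazard ratio of 1.5. At 2.5 it is 72.3% and 75.5%, with type I error 4.2% and 5.0%. The pattern is the same.

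**The case against.** The strongest reply is that this reads a specification into silence, for p-values on which nothing depends. Four parts of it stand.

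- **The SAP never says the test is unstratified.** A reader might infer that a plain test was prescribed. That is the natural reading, because sections 3.1, 3.2 and 4.1 of the same appendix name their strata and section 2.1 does not. It is still an inference. Since SAP 5.2.4 speaks of most analyses, a plain test would not contradict it.
- **No log-rank test is named for the section 2.2 curves.** It reaches them only through the reference to similar tables and the matching table pairs in Appendix 4. The simulation does not cover them: they run to 496 minutes, censor at rescue, and for three symptoms use subsets of the mITT population.
- **The power loss is conditional.** With no prognostic effect there is none. Losses above about 3 points appear only at a hazard ratio of 3 in some settings, and the documents give no basis for assuming so strong a factor.
- **Stratification would not reconcile the curves with the binary results.** A reader might blame any disagreement on the missing strata. For the symptoms the larger reasons are that the binary analyses look at a fixed time and count rescue as failure, while the curves use event times up to 8 hours and censor at rescue.

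It is also fair that Appendix 3 is written in the past tense. If the analyses have been run, replacing the test would be a further post-hoc choice.

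What does not stand is the conclusion that clarification alone is enough. Stratifying by the randomization factor follows the SAP's own reasoning in 5.2.4, and it cost essentially no power in the settings where the factor had no effect.

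**Conclusion.** The point holds as a minor improvement. Appendix 3, section 2.1 gives a log-rank p-value with no stratification, and section 2.2 appears to extend it to the other curves, although randomization and the risk-difference analyses are stratified by prophylaxis. If prophylaxis is prognostic, a plain test is conservative. For time to rescue the loss is nil at an assumed hazard ratio of 1, under 1 point at 1.5 and about 1 to 3 points at 2. These sizes rest on assumed event rates, prevalence and treatment effects, and on exact balance within strata, which mITT subjects will meet only approximately.

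The documents do not support reading this as a threat to the trial's conclusions. The analyses are supportive and outside the fixed sequence, SAP 5.2.5 treats exploratory p-values as descriptive, and the confirmatory rescue comparison is already stratified. The direction of any error is conservative.

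**What to change.** In Appendix 3, sections 2.1 and 2.2:

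1. State which curves carry a log-rank p-value, including whether the nominal-time set does.
2. Specify the log-rank test stratified by use of prophylactic migraine medication (yes/no). Pool the strata when one has fewer than 5 subjects, as in SAP 5.7.3.1.
3. If a plain test has already been run, keep it, report the stratified test beside it, and label it as added later.

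The cost is a sentence or two of text and one strata specification in the program. If results already exist, there is one extra p-value in each affected table. The Kaplan-Meier curves and medians need not change.

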2.2 Time to First Report of Absence of Various Symptoms

For each of the following variables, two sets of Kaplan-Meier plots and tables were created:

- Time to First Report of Absence of Most Bothersome Symptom
- Time to First Report of Absence of Nausea
- Time to First Report of Absence of Photophobia
- Time to First Report of Absence of Phonophobia
- Time to First Report of Return to Normal Functioning

The first set of plots and tables was similar to those created for the time to rescue medication (using actual time). For the second set of plots, nominal (planned time point) as opposed to actual time was used for clinical event times. Censoring was measured using actual time as in all previous plots.

For both sets of analyses, the analysis population for MBS and functional disability was the set of mITT subjects. The analysis population for nausea, phonophobia, and photophobia was the subset of mITT subjects that reported the symptom as present at the onset of their study migraine. The y-axis for all plots represents the probability of the occurrence of the event of interest, and therefore are increasing from left to right.

2.2.1 Kaplan-Meier Plots and Tables: Actual Time for Event of Interest

The first set of K-M plots and tables were created using actual time of censoring and actual time for the clinical event of interest. Subjects were censored at the actual time of their first use of rescue medication or last reported data point if lost to follow-up. Subjects who did not have the clinical event of interest by 8 hours post dose were censored at 496 minutes (480 minutes + 15 minute window + 1 minute).

